10	beta	1.5h	4.0000	-0.1160	0.2670	0.5339	-0.7568	0.9151	-0.4345	0.6639
11	beta	2h	4.0000	0.1975	0.0876	0.1752	0.3639	0.1315	2.2550	0.0241
12	beta	6h	3.0000	0.4717	0.0572	0.0991	0.5910	0.0519	8.2431	0.0000
13	beta	8h	4.0000	0.5715	0.1271	0.2542	0.6648	0.0550	4.4960	0.0000
14	beta	0h	4.0000	0.1092	0.1134	0.2268	0.1425	0.2227	0.9632	0.3354
15	beta	12h	4.0000	0.4620	0.0581	0.1161	0.6040	0.0604	7.9570	0.0000
16	beta	1h	4.0000	-0.4895	0.1652	0.3304	-1.4024	0.6361	-2.9635	0.0030
17	beta	3h	4.0000	2.2147	1.9988	3.9977	0.5025	0.1616	1.1080	0.2679
18	beta	4h	4.0000	0.0277	0.3313	0.6626	-0.2181	0.2404	0.0838	0.9332

The results of the 10 days at 8 hours on sAPP α and β is SD = 0.1695.

Assuming type one error, $\alpha=0.05$ and type two error, $\beta=0.2$, or a power of 0.8, the calculated sample range of delta effect sizes was 0.3 to 2 SD.

	delta	standardized_delta	N
1	0.08	0.30	175.00
2	0.10	0.40	99.00
3	0.13	0.50	64.00
4	0.15	0.60	45.00
5	0.18	0.70	39.00
6	0.20	0.80	26.00
7	0.23	0.90	20.00
8	0.25	1.00	17.00
9	0.28	1.10	14.00
10	0.31	1.20	12.00
11	0.33	1.30	10.00
12	0.36	1.40	9.00
13	0.38	1.50	8.00
14	0.41	1.60	7.00
15	0.43	1.70	7.00
16	0.46	1.80	6.00
17	0.48	1.90	5.00
18	0.51	2.00	5.00

sAPP α

Using the above data, we can calculate that a power analysis of APP α shows the requirement of 9 people to see a 36% change in sAPP α levels at a statistical significance level of >0.05

delta	standardized_delta	N
1	0.05	175.00
2	0.07	99.00
3	0.08	64.00
4	0.10	45.00
5	0.12	33.00
6	0.14	26.00
7	0.15	20.00
8	0.17	17.00
9	0.19	14.00
10	0.20	12.00
11	0.22	10.00
12	0.24	9.00
13	0.25	8.00
14	0.27	7.00
15	0.29	7.00
16	0.31	6.00
17	0.32	5.00
18	0.34	5.00

sAPP β

Using the above data, we can calculate that a power analysis of APP β shows the requirement of 9 people to see a 24% change in sAPP β levels at a statistical significance level of >0.05 . We are expecting changes in sAPP α and β levels to be between 20 and 50% and for the higher doses an $n < 5$ would be adequate to detect those changes.

aSYN

However, we do not expect the changes in alpha-synuclein and in neurotransmitters to be that pronounced. Therefore, we chose an $n=10$. If dropouts are to occur, they will be replaced to allow the full sample size of 5×10 participants to be achieved.

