From a scheduling perspective, four separate analyses will be performed. The first once the first cohort of 14 PD patients have completed Part 1 and the second once the second cohort of 14 AD patients complete Part 1. The third analysis will be carried out when the third cohort (4 treatment groups) in Part 2 has completed all assessments but this will also include the Placebo and 80mg posiphen patients from the Part 1 PD cohort. The fourth analysis will include the pharmacokinetic data from both Part 1 (AD and PD patients) and Part 2 (PD patients), and, if required, a presentation of the results from the evaluation of infective particles in CSF and exosomes in plasma.

Given the study design (patient type and treatment dose) all safety evaluations will be reported separately in each of the first three analyses.

The following study documents were used for the preparation of this SAP:

- ANVS-12003_AD-PD-CSFProtocol_v3_8-21-2020 (protocol)
- ANVS 12003 (Annov 251151) SDTM 3.2 Annotated CRF v0.4 20200902

The example layouts of the data presentations are shown in Appendices 1-3 for tables, figures and listings, respectively.

2. Objectives.

A broad range of objectives are specified in this early stage exploratory investigation. They include safety and tolerability in both patient groups (AD and PD). Pharmacodynamics and early Efficacy indicators with biomarker target engagement, pathway engagement and functional/cognitive measures respectively across both Part 1 and 2 of the study.

Drug pharmacokinetics in CSF and blood will also be characterised at the dose selected in AD and PD patients in Part 1 and across the range of doses selected in PD patients in Part 2.

Part 1 - Safety, tolerability, pharmacodynamics, efficacy and pharmacokinetics of posiphen (80mg QD after 25 days) in early AD and PD patients.

Part 2 - Safety, tolerability, pharmacodynamics, efficacy and pharmacokinetics of posiphen (5, 10, 20, 40mg QD after 25 days) in early PD patients.

The primary comparisons of interest performed in Part 1 and Part 2 are the changes from baseline (Within treatment group). The null hypothesis throughout is that there is no difference between the Day 25 end of treatment and Pre-treatment baseline ($H_0. X_{end}=X_{base}$, $H_1. X_{end} \neq X_{base}$).

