Between treatment group comparisons will also be done (but are of secondary interest due to the small sample size). Here, the null hypothesis is that there is no difference between any of the treatment groups at the end of treatment ($H_0. Placebo=X_{5mg}=X_{10mg}=X_{20mg}=X_{40mg}=X_{80mg}$, $H_1. Placebo \neq X_{5mg} \neq X_{10mg} \neq X_{20mg} \neq X_{40mg} \neq X_{80mg}$).

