3.1 Power and Sample Size Determination

This is an exploratory investigation of safety, tolerability, pharmacokinetics, pharmacodynamics and efficacy focusing on target engagement, pathway engagement and functional/cognitive measures. Ten patients per dose group will provide sufficient data to demonstrate within group changes for sAPP α and sAPP β to be of the order of 20-40% (see Table 1 below) and to characterise the PK of posiphen and support potential dose proportionality analyses.

Table 1: Sample Size Estimation

Biomarker	SD	Delta effect size	Within treatment group change	N/Group*
sAPP α	0.1695	0.3 to 2 SD	36%	9
sAPP β	0.1695	0.3 to 2 SD	24%	9

*With 80% power and 0.05 two tailed significance level

NB. Alpha-synuclein (aSYN) and in neurotransmitters provide valuable supporting information but changes are anticipated to be smaller and would require larger group sizes.

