6.1 Pharmacodynamic Endpoints

For the Part 1 AD and Part 1 PD cohorts, each variable measured in plasma and CSF will be analysed using an analysis of variance (ANOVA) model of the percentage changes from Baseline (between Baseline Day 0 Pre-dose 0h and Day 25 Pre-dose 0h). This will include Treatment group as a fixed effect and LSmeans (with 95% CI) for this effect will be presented (Within group).

Between group differences for 80mg vs Placebo will be assessed and presented (LSmeans +/- 95% CI) although results will be viewed cautiously given small control group samples size.

Then the percentage change from Baseline (Day 25 Pre-dose 0h) for each of the 6 hourly assessments will be analysed using a Repeated measured mixed model (RMMM) including Treatment group as a fixed effect, Time as the repeated effect and Subject as random term. Compound symmetry will be assumed for the covariance/correlation matrix. An overall average LSmean (with 95% CI) for the Treatment effect will be presented together with individual LSmean (with 95% CI) estimates for each hour. Treatment group differences will also be presented for the comparison between 80mg vs Placebo but the same caveat used given the control group subject sample size.

The maximum percentage change from Baseline (Day 25 Pre-dose 0h) over the 6 hours will also be analysed with an ANOVA model for both the Within treatment group and Between group (80mg vs Placebo) comparisons.

In the event of either model failing assumptions of normality or constant variance, a log transformed analysis of the actual values (*not percentage change*) will be substituted and the output estimates (means and 95% CIs) then back transformed by exponentiation to enable presentation of the ratio of values (%).

For the Part 2 PD cohort with 4 treatment dose groups (5, 10, 20, 40mg) the same analyses models will be employed. However, the data from the Part 1 PD patients will also be included (for those biomarker variables retained from Part 1 after evaluation at that stage) from both the Placebo and 80mg patient groups and combined with the Part 2 data. Within and Between group ANOVAs and RMMM model analyses will then be employed in a similar manner to Part 1. The Part 2 report of treatment group differences will include Placebo (from Part 1) versus each of the five active treatment groups, namely 5mg, 10mg, 20mg and 40mg from Part 2, and 80mg group from Part 1.

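### SAP Table 1 gives N = 9 as the size for a within-group change, but that N is the per-arm size for comparing two equal independent arms

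*SAP*

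**What the plan says.** Protocol 6.2 takes 80% power, "or a power of 0.8, the calculated sample range of delta effect sizes was 0.3 to 2 SD", and prints two grids of N against effect size. It does not name the test. Row 12 of the first grid (delta 0.36, 1.40 SD, N = 9) gives the sAPPα statement, "the requirement of 9 people to see a 36% change". Row 12 of the second grid (delta 0.24, N = 9) gives the matching sAPPβ statement for 24%. Both sentences print the significance level as greater than 0.05.

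SAP 3.1 says "Ten patients per dose group will provide sufficient data to demonstrate within group changes for sAPP" α and β. Table 1 then lists SD 0.1695 and N = 9 per group for both biomarkers, in a column for the change within a treatment group, with the footnote "With 80% power and 0.05 two tailed significance level".

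SAP 2 and 6 make the within-group change from baseline the comparison of primary interest. Between-group comparisons are also done, "but are of secondary interest due to the small sample size". For Part 1, SAP 6.1 adds that "Between group differences for 80mg vs Placebo will be assessed and presented", to be read with caution because the control group is small. SAP 3.3 sets the Part 1 allocation at 10 active to 4 placebo in each cohort.

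**The concern.** A within-group change is tested on one sample of paired differences, and a treatment difference is tested on two independent samples. At the same standardized effect, the two-sample test needs roughly one and a half to two times as many patients per group over most of this grid. A sample size carried from one test to the other no longer has its stated power.

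Table 1 is the only quantitative power statement in either document, and it supports the comparison that the SAP ranks first. If its N, power and test do not fit together, a reader cannot tell from it what size of biomarker change the study could miss.

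**Working it through.** **Inputs.** Two-sided α = 0.05, power 0.80 (SAP Table 1). Effect 1.40 SD (Protocol 6.2, row 12 of the first grid). The second grid's standardized column is missing from the text available, so 1.40 is inferred for its row 12 from the matching row order and N. SDs of the 8 h change, four patients each (Protocol 6.2): sAPPα 0.1695, sAPPβ 0.2542. Planned n: 10 per dose group, 4 placebo per Part 1 cohort.

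These are SDs of within-patient change. The source table lists them beside the mean change, and for sAPPα SE × √n = 0.0847 × √4 = 0.169.

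**Formulas.** Power = P(T > t(0.975, df)), where T is noncentral t with df degrees of freedom and noncentrality λ:

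- two independent arms: λ = d·√(n₁n₂/(n₁+n₂)), df = n₁+n₂−2
- one sample of changes: λ = d·√n, df = n−1

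**Step 1: reproduce the printed grid.** N solving for 80% power:

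| Effect (SD) | Printed N | Two-sample, per arm | One-sample |
|---|---|---|---|
| 0.3 | 175 | 175.4 | 89.2 |
| 0.5 | 64 | 63.8 | 33.4 |
| 0.7 | 39 / 33 | 33.0 | 18.0 |
| 1.0 | 17 | 16.7 | 9.9 |
| 1.4 | 9 | 9.08 | 6.2 |
| 2.0 | 5 | 5.09 | 4.2 |

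All 18 rows of the second grid match the two-sample column to rounding. The first grid differs only at 0.7 SD, where it prints 39 against 33 in the second. The one-sample N is lower in every row. With 9 per arm, λ = 1.4 × √4.5 = 2.97 on 16 df, and power is 79.6%.

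**Step 2: the test named in Table 1, at 1.4 SD.**

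- n = 6: 78%; n = 7: 87%. So 7 patients suffice.
- n = 9: λ = 1.4 × 3 = 4.20, 8 df, power 95.5%.
- n = 10: λ = 1.4 × 3.162 = 4.43, 9 df, power 97%.
- N = 9 gives exactly 80% only at a two-sided α of 0.012.

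**Step 3: the percent changes as printed.** The grids imply SDs of 0.36/1.40 = 0.257 for sAPPα and 0.24/1.40 = 0.171 for sAPPβ. These are close to the other biomarker's SD (0.2542 and 0.1695).

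- sAPPα with the SD in Table 1: 0.36/0.1695 = 2.12 SD, not 1.4.
- sAPPβ with its own SD: 0.24/0.2542 = 0.94 SD. One-sample power is 70% at n = 9 (λ = 2.83) and 76% at n = 10 (λ = 2.99); 11 patients are needed for 80%.

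**Step 4: what n = 10 detects within group at 80% power.** SAP 6.1 plans LS means from an ANOVA with treatment as a fixed effect, so the error df can exceed 9. Part 1 has 14 − 2 = 12 df. The combined PD analysis has 54 − 6 = 48 df.

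| Error term | Detectable change |
|---|---|
| One-sample t, 9 df | 1.00 SD |
| Part 1 ANOVA, 12 df | 0.97 SD |
| Pooled Part 2 ANOVA, 48 df | 0.90 SD |

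With λ = 2.99 and these larger df, sAPPβ power at 0.94 SD and n = 10 becomes 78% (12 df) or 83% (48 df).

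**Step 5: 10 versus 4, for information.** √(10×4/14) = 1.690, so λ at 1.4 SD = 2.37. Power is 59% (12 df) or 64% (48 df). The effect detectable with 80% power is 1.81 SD (12 df) or 1.69 SD (48 df).

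**The case against.** The strongest reply is that the mislabelling does no harm to the primary comparison. The SAP's operative claim is that ten patients are enough to show within-group change, and at 1.4 SD they are more than enough. The study is exploratory, its primary outcomes are safety, tolerability and PK, and the protocol chose 10 for PK and because smaller changes in alpha-synuclein were expected. The 9 did not set enrolment. All of this stands, and it limits the point to a correction of the stated figures.

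A reader might infer three stronger things that the documents do not support.

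- *That Table 1 is impossible, or that the within-group test is underpowered throughout.* At 1.4 SD the printed N errs on the safe side.
- *That the 80 mg versus placebo comparison falls short of a promised 80%.* No document gives it a power. The SAP calls it secondary because of the sample size and says it will be read cautiously. The 59% contradicts no printed figure.
- *That within-group power is always higher than printed.* It is at 1.4 SD, but not for a 0.24 change in sAPPβ with that biomarker's own SD and a one-sample test.

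It can also be objected that a one-sample t-test is not the planned ANOVA. That is right, and for this reason the figures are given for each error term.

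**Conclusion.** The point holds as a mismatch between test, N and power. N = 9 at 80% power and two-sided 0.05 belongs to a comparison of two equal independent arms, and Table 1 attributes it to a within-group change. At 1.4 SD the named test needs 7 patients and has about 96% power with 9. The identity of the grid does not depend on any SD or unit.

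The direction of the error in power does depend on the SD, and these SDs come from four patients each. It also rests on reading 0.1695 as an SD of change, as the source table indicates. If it were a single-visit SD, the standardized change would be 1.4/√(2(1−ρ)), with ρ the correlation between visits. Power at n = 9 would then be 74%, 85%, 95.5% or 99.9% for ρ = 0, 0.25, 0.5 or 0.75. The ANOVA figures assume equal variance across groups.

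**What to change.** In SAP Table 1 and Protocol 6.2, name the test and replace the N = 9 rows with SD-scale figures for the planned n = 10. Suggested wording:

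> Within-group change from baseline, two-sided 0.05, n = 10: 80% power for a mean change of 1.0 SD of the within-patient change (one-sample t, 9 df; about 0.97 SD with the Part 1 ANOVA error on 12 df, and 0.90 SD with the pooled Part 2 error on 48 df). For information, 80 mg versus placebo (10 versus 4): 80% power for about 1.8 SD in Part 1 (12 df) and 1.7 SD with the pooled Part 2 error (48 df); at 1.4 SD, power is about 59% and 64%.

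If percent changes are kept, recompute each row from that biomarker's own SD, with the change and the SD on the same scale. Do not carry 1.4 SD forward as the planned effect for both biomarkers. In the same edit, give the protocol's significance level as two-sided 0.05 and reconcile the 0.7 SD row (39 against 33).

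The cost is one table and a few sentences. Enrolment and analysis do not change. The sponsor would be stating a less favourable figure for sAPPβ unless the pooled Part 2 error is used, and would be disclosing a limited placebo comparison in numbers.

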3.2 Interim analysis

No interim analysis is planned.

However, on completion of Part 1, the biomarkers in the plasma and CSF samples will be analysed unblinded to determine what changes are needed to the biomarkers to be measured in Part 2. Since the conduct of the study in Part 2 will be identical to the conduct of the study in Part 1, recruitment will continue uninterrupted. The only potential change between Part 1 and Part 2 are the actual biomarkers to be measured. Due to COVID-19 causing recruitment challenges, at the time of intended analysis, Part 1 will now be analysed according to cohort. Therefore, the first analysis will occur after 14 PD patients have completed Part 1 and a second analysis will occur when 14 AD patients have completed Part 1.

3.3 Randomisation

For Part 1: For each cohort (AD, PD) up to 14 subjects will be randomised to posiphen or placebo in a ratio of 10 Active: 4 Placebo.

For Part 2: A sample size of up to 40 Early PD patients will be randomized to one of the 4 posiphen doses, 10 patients each dosed at 5 mg, 10 mg, 20 mg, or 40 mg.

The study is conducted in a blind manner and the randomization schedule for each cohort will be available once all patients in each cohort have completed the required schedule and the data have been locked for that cohort.

4. Population

Three analysis populations are defined for each of the three cohorts (Part 1 AD, Part 1 PD, Part 2 PD):

Intent to treat population

The Intention to treat population (ITT) includes all patients who received at least one dose of study medication and provide post baseline data. Analyses will be based on the treatment actually received and not necessarily that scheduled by the randomisation.

Safety population

The Safety population (Safety) includes all patients who received at least one dose of the study medication. Summaries of safety and tolerability will be based on the actual treatment received.

Pharmacokinetics population

The Pharmacokinetic population (PK) includes all patients who receive at least one dose of study medication and who provide sufficient data to enable parameter estimation.

5. Study Methods

Assessments will be made during three visits (Screening, Baseline and Confinement); in addition there are two telephone calls to assess for adverse events. Specific clinic procedures and details of all assessments performed are given in Section 9 of the protocol.

5.1 Schedule.

Details of all assessments performed with timings are given in Table 2.

Table 2: Clinical Assessments Schedule

Visit Timing	Day -42 to 0		Day 14 (± 4)	1-3 days prior to confinement	Days 25 (± 2)		
Procedures	Screening	Baseline	Phone	Pre- Confinement Phone Contact	Confinement		
					Admission	6-Hour Sampling	Discharge ^e
Informed Consent	X						
Demographics	X						
Medical and Psychiatric History	X						
Height and BMI	X						
Inclusion and Exclusion Criteria	X	X					
Urine Dipstick Pregnancy Test	X						
Physical and Neurological Examination	X	X			X		X
AD & PD: MMSE	X	X			X		
AD: CDR	X	X			X		
AD: ADAS-Cog 14		X			X		
AD & PD: WAIS-IV		X			X		
PD: MDS-UPDRS	X ^g	X			X		
C-SSRS	X	X			X		
Vital Signs ^b	X	X			X	X	X
Clinical Lab Safety Tests	X	X ⁱ			X ⁱ		
12-Lead ECG	X	X			X		X
MRI of Brain ^c	X						
Adverse Events	X	X	X	X	X	X	X
Prior/Concomitant Medication	X	X	X	X	X	X	X
Randomization		X					
Dispense Study Drug		X					
Dosing Study Drug in Clinic		X					X
Study Drug Compliance Check			X	X	X		
APOE Genotype and DNA Markers		X					
Blood Sampling for PK		X					X
Lumbar Puncture for baseline Pharmacodynamics		X					
LP Catheter Placement ^h					X		
Collecting blood and CSF for Biomarkers in Plasma and CSF		X				X ^f	
24-Hour Phone Follow-Up ^d		X					X
Lumbar Xray ^h (Optional)	X						

^a Refer to Section 9 for more details on visit timing and windows.

^b Vital signs will include sitting blood pressure, pulse, temperature, respiration rate, and weight, except during the 6-hour Sampling Phase of the Confinement Visit when weight will not be included.

^c An MRI of the brain will only be conducted if there is no brain MRI available from within the window specified in Inclusion Criteria.

^d Phone Follow-up should occur approximately 24-hours after completion of the LP procedure at Baseline and after discharge from the Confinement Visit.

^e The Early Discontinuation Visit will contain the same assessments as the Pre-confinement Visit.

^f Sampling Times: 0,1,2,3,4,5,6 hrs (±10 mins for collection)

^g Hoehn & Yahr Stage only for inclusion determination

^h X-Ray is only required if LP insertion will not be performed with fluoroscopy

ⁱ Safety labs at baseline and confinement (for sample 0 hour) should be taken fasted

5.2 Treatment Measures.

Treatment measures are evaluated by pharmacodynamics and by efficacy endpoints.

5.2.1 Pharmacodynamic Endpoints

Pharmacodynamic endpoints are based on the assessments from protein levels in blood, plasma and CSF at the Baseline (0h Pre-dosing) and Day 25 (Confinement) visit (0h Pre-dosing, 1, 2, 3, 4, 5, 6h). Pre-dosing values at Baseline will be compared with Day 25 (Confinement) and derived as a percentage change from Baseline. The Percentage change from Day 25 0h pre-dose at 1, 2, 3, 4, 5 and 6h on Day 25 (Confinement) will also be derived and presented. The maximum percentage change determined over the 6h period may also be incorporated.

Table 3: Pharmacodynamic Endpoints

Pharmacodynamic measure	CSF	Plasma
Target Engagement		
aSYN monomers	X	
Aβ monomers:		
A β 40	X	X
A β 42	X	X
Soluble Amyloid Precursor Proteins:		
sAPP α	X	
sAPP β	X	
Tau Proteins:		
T-tau	X	X
P-tau	X	X
Pathway Engagement		
Axonal Transport:		
Neurofilament light (NfL)	X	X
Inflammatory factors:		
Complement 3	X	

	YKL40	X	
	sTREM2	X	
	GFAp	X	X
Synaptic factors:			
	SNAP25	X	
	Synaptotagmin	X	
	Neurogranin	X	
Control proteins:			
	Beta-trace protein	X	
Infective particles:			
	aSYN oligomers	X	
	A β oligomers	X	
Exosomes			X

5.2.2 Efficacy - Functional/Cognitive Measures

Patients will complete the appropriate questionnaires at Baseline and Day 25 (Confinement). For each, the Total score and, where appropriate the item/domain scores, will be calculated, and the Change from Baseline derived. Actual scores and Effect sizes ($(X_{\text{Base}} - X_{\text{Day25}})/SD$) will be presented.

MMSE is a 30 point test that is widely used for cognitive function that includes tests of orientation, attention, memory, language and visual-spatial skills.

WAIS-IV is a test to assess cognitive ability in adults which helps to examine the relationship between intellectual function and memory in seven subtests: Spatial Addition, Symbol Span, Design Memory, General Cognitive Screener, Logical Memory (I & II), Verbal Paired Associates (I & II), and Visual Reproduction (I & II). Performance is reported as five Index Scores: Auditory Memory, Visual Memory, Visual Working Memory, Immediate Memory, and Delayed Memory. Patients will be scored on the number of correct items from images and words shown in the space of two minutes.

MDS-UPDRS has four parts: Part 1 – non-motor experiences of daily living (13 items), Part 2 - motor experiences of daily living (13 items), and Part 3 – motor examination (20 scores based on 18 items plus Hoehn and Yahr Stage) and Part 4 – motor complications (6

questions). Each item is scored on a scale of 0 (normal) to 4 (severe). Scores from each part of the scale are combined to provide a total score.

ADAS-Cog14 is a test to evaluate cognition and differentiates between normal and impaired cognitive functioning by using a number of tests to assess memory, language and comprehension. Different Word lists were used in different countries to allow for language differences but validated versions were always used and always presented in the correct and standardised manner.

CDR is a global summary to identify the overall severity of dementia from domains; Memory, Orientation, Judgement and Problem solving, Community Affairs, Home and Hobbies and Personal care, each of which is rated on a 5 point score.

Table 4: Clinical Function and Cognitive Endpoint Scoring

Efficacy		Score Range (units)	Scale Direction
Cognitive Function Tests			
WAIS-IV	Total Score	Scaled Score 0 - 100	High score best
ADAS-cog14 (14 items)	Total Score (Count incorrect items)	0 - 90	Low score best (0=All correct)
ADAS-cog11 (11 items)	Total Score (Count incorrect items) Includes: Word Recall, Naming Objects and Fingers, Commands, Constructional Praxis, Ideational Praxis, Orientation, Word Recognition, Language, Comprehension of Spoken Language, Word Finding Difficulty and Remembering Test Instructions	0 - 70	Low score best (0=All correct)
ADAS-cog 6 (6 items)	Total Score (Count incorrect items) Includes Word Recall, Naming Objects and Fingers, Commands, Constructional Praxis, Orientation, and Word Recognition Score	0 - 45	Low score best (0=All correct)
ADAS-cog 3 (Memory) (3 items)	Total Score (Count incorrect items) Includes Word Recall, Orientation, and Word Recognition	0 - 30	Low score best (0=All correct)
CDR	Individual item scores: Memory, orientation, judgement and problem solving, community affairs, home and hobbies, and personal care	0 = Normal 0.5 = Very Mild Dementia 1 = Mild Dementia 2 = Moderate Dementia 3 = Severe Dementia	Global Summary Score range = 0 – 3 Low score best

	Sum of Boxes (Total Score)	0 - 18	Low score best
Non-Motor Experiences and Motor Function			
MDS-UPDRS	Individual scores	0 =Normal 1 = Slight 2 = Mild 3 = Moderate 4 = Severe	Low score best
	Total Score	0 - 208	Low score best
	Part 1 – non-motor experiences of daily living	0 -52	Low score best
	Part 2 - motor experiences of daily living	0 -52	Low score best
	Part 3 – motor examination	0 -72	Low score best
	Part 4 – motor complications	0 -24	Low score best
Hoehn and Yahr		0 = Asymptomatic 1 = Unilateral involvement only 2 = Bilateral involvement without any impaired balance 3 = Severe disability 4 – Wheelchair bound or bedridden unless aided	Low score best
Disease Staging			
MMSE	Total Score (Count correct items)	0 - 30	High score best (0=Severe impairment / 30=No impairment)
	Categorical scores	24– 30 18 - 23 0 - 17	No cognitive impairment Mild cognitive impairment Severe cognitive impairment

5.3 Safety Measures.

Drug safety is assessed by monitoring adverse events, vital signs, physical examinations, 12-lead ECG, and concomitant medication data. These are supported by laboratory data assessments of blood and urine providing serum chemistry, haematology and urinalysis

evaluations. Patients will also use the Columbia suicide rating scale (C-SSRS) as an additional safety assessment on entry and at the confinement visit.

All reported adverse events will be coded into system organ class (SOC) and preferred term (PT) using the MedDRA dictionary version 23. The number of patients reporting adverse events during either the dosing or follow up periods is summarised according to the coded system organ class (SOC) and preferred term (PT). All adverse events are coded individually, even where combination events are reported simultaneously.

Adverse events starting or pre-existing events with an increase in severity on or after the first dose of study IMP are defined as treatment emergent adverse events (TEAE). An event starting before the first dose of study IMP will be identified as a pre-treatment sign or symptom (PTSS).

All laboratory data will be merged with the subject Case Report Form (CRF) database and summarised. Laboratory values will be defined as clinically significant according to the pre-specified abnormal limits, and will be summarised and listed by subject.

The Columbia suicide rating scale is a series of six questions in which the patient is asked to indicate whether they have experienced several thoughts or feelings relating to suicide over the past month. The responses to each question by patients in each cohort will be summarised by treatment group and visit.

